- a. Male
- b. Female

2. How old is your child? _____ years

3. What is your child's race?

- a. White/Caucasian
- b. Black/African American
- c. Asian
- d. Mixed race
- e. Other, please specify _____
- f. Prefer not to answer

4. Is your child Hispanic?

- a. Yes
- b. No

5. Is your child eligible for free or reduced-price lunch?

- a. Yes
- b. No

6. Were you born in the United States?

- a. Yes
- b. No

If no, where were you born? _____

When did you move to the United States? _____

7. Was your child born in the United States?

- a. Yes
- b. No

If no, where was your child born? _____

When did you move to the United States? _____

Compliance Questionnaire

1. Did you drink the assigned study beverages {insert specific type for participant per randomization} today? If so, how many?

Please circle: YES or NO

Quantity: _____ cans OR _____ ounces

Brand and name of beverage:

2. Did you drink any other sugar beverages today? If so, which ones and how many/how much?

Please circle: YES or NO

Quantity: _____ cans OR _____ ounces

Brand and name of beverage:

3. Did you drink juice today? If so, what kind and how much?

Please circle: YES or NO

Quantity: _____ cans OR _____ ounces

Brand and name of beverage:

4. Did you have any caffeinated beverages, such as coffee, tea, or hot chocolate today? If so, which ones and how many/how much?

Please circle: YES or NO

Quantity: _____ cans OR _____ ounces

Brand and name of beverage:

Beverage Questionnaire

Name: _____

Date: _____

Instructions

In the past month, please indicate your response for each beverage type by marking an "X" in the square for "how often" and "how much each time".

1. Indicate how often you drank the following beverages, for example, if you drank 5 glasses of water per week, mark 4-8 times per week.
2. Indicate the approximate amount of beverage you drank each time, for example, if you drank 1 cup of water each time, mark 1 cup under "how much each time".
3. Do not count beverages used in cooking or other preparations, such as milk in cereal.
4. Count milk added to tea and coffee in the tea/coffee with cream beverage category NOT in the milk categories

Type of Beverage/Drink	HOW OFTEN (MARK ONE)							HOW MUCH EACH TIME (MARK ONE)				
	Never or less than 1 time per week (go to next drink)	1 time per week	2-3 times per week	4-6 times per week	1 time per day	2+ times per day	3+ times per day	Less than 6 fl oz (3/4 cup)	8 fl oz (1 cup)	12 fl oz (1 1/2 Cups or 1 soda can)	16 fl oz (2 cups or 1 soda bottle)	More than 20 fl oz (2 1/2 cups)
Water (plain/unsweetened, water or seltzer)												
100% Fruit Juice												
Sweetened Juice Drinks (e.g. fruit drinks such as KoolAid, lemonade, punch, Sunny Delight)												
Diet Fruit Drinks (e.g. light lemonade, light juice drinks)												
Whole Milk												
Reduced Fat Milk (2%)												
Low Fat/Fat Free Milk (Skim, 1%, Buttermilk, Soy milk)												
Regular, caffeinated, Soft Drinks/ Regular Soda with caffeine (e.g. Coke, Pepsi, Mountain Dew)												
Caffeine-free Regular Soft Drinks/Soda (e.g. Sprite, Fanta, Caffeine-free Coke)												
Diet/Artificially Sweetened Soft Drinks including diet soda, (e.g. Diet Coke, Diet Pepsi, Coke Zero)												
Caffeine-free Artificially Sweetened Soft Drinks/Soda (e.g. Caffeine-free Diet Pepsi, Diet Sierra Mist, Sprite Zero)												
Sweet Tea (e.g. Arizona Iced Tea, Nestea, Pure Leaf)												
Diet Iced Tea (e.g. Diet Snapple, Diet Nestea)												
Hot Tea or Coffee, with cream and/or sugar												
Hot Tea or Coffee, black, without artificial sweetener (no cream or sugar)												
Hot Tea or Coffee, black, with artificial sweetener (e.g. Splenda, Equal, Sweet N' Low)												
Energy Drinks (e.g. Red Bull, Rockstar, Monster, etc.)												
Diet/Artificially Sweetened Energy Drinks (e.g. sugar-free RedBull, Monster Zero)												
Sports Drinks (e.g. Gatorade, Powerade, etc.)												
Diet/Artificially Sweetened Sports Drinks (e.g. Powerade Zero, G2)												

IRB NUMBER: NCR191271
 IRB APPROVAL DATE: 06/07/2019

Beverage Taste Testing Form

Instructions for Pediatric Subjects. Show the cups to the subject and say: "We're going to play a game with things to taste. Here are two cups. You will taste what's inside the first cup, swish it around your mouth (BUT don't swallow) and I will tell you when to spit it out in the big cup. You will then rinse your mouth with water and then taste what's inside the second cup. I will tell you when to spit it out. Then I want you to POINT TO which one you like better - the first one or the second one. You will then rinse your mouth 2 times with water and we will do this again."

Notes:

- Be sure to underline which concentration is in position 1 for each pair.
- Use stopwatch to time solution in mouth for 5 seconds, and 1 minute between pairs
- Circle the

	Which one do you like better?				Which one is sweeter?				Notes
	A	B	C	D	A	B	C	D	
1.									
2.									
3.									
4.									
5.									
6.									

Qualitative Interview/Debrief Questions

- a) How difficult was it for your child to drink only the study drinks?
- b) Were other sodas/sugar-sweetened beverages available in the house during the intervention?
- c) Did your child drink these other beverages? How much do you think?
- d) How much oversight do you have over their beverage intake? Do you think they got other beverages elsewhere? Did they sneak soda/sugar-sweetened beverages?
- e) Did your consumption change at all as a result of participating in this study? How so?
- f) What was the hardest part of participating in this study?
- g) What was the best part of participating in this study?
- h) Anything else that you can tell us about your experience in this study?

Reminder Messages

The following reminders will be sent to parents during the intervention:

“Hi ___[insert parent name]__. This is a friendly reminder to please complete the study questionnaires.”

“Hi ___[insert parent name]__. This is a friendly reminder to please remind ___[insert child name]_ to drink only the study drinks provided until ___[insert date of follow-up visit]__.”

DOES YOUR CHILD LIKE SODA OR SWEET TEA?

RECRUITING CHILDREN 8-11 YEARS OLD

Please consider participating in our study!

\$175 Compensation

- **What does participating involve?**
The study involves asking your child to drink sugar-free and/or caffeine free soft drinks for two weeks. We will ask your child to complete daily questionnaires and participate in telephone interviews about their diet for three weeks.
- **Is my child eligible?**
Your child may be eligible if they are 8-11 years old and drink at least 12 ounces of sugar sweetened caffeinated beverages per day.

**For more information, contact The George Washington University
study team at: [contact].**

¿LES GUSTAN A SUS HIJOS SODA O TÉ DULCE?

Reclutando a Niños 8-11 años

Por favor, considere participar en nuestro estudio.

\$175 de Reembolso

- **¿Que implica participar?**
El estudio implica pedir a su hijo tomar bebidas sin azúcar y/o cafeína por dos semanas. Pediremos que su hijo complete cuestionarios diarios y participe en entrevistas telefónicas sobre su dieta por tres semanas.
- **¿Es elegible mi hijo?**
Su hijo pueda ser elegible si tiene 8-11 años y si tome por lo menos 12 onzas de bebidas azucaradas con cafeína cada día

**Para más información, por favor, contactor el equipo de estudio del
George Washington University a: [contact]**

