Lowering SSB consumption is a central component of lifestyle behavior change aimed at preventing and managing obesity,⁵ yet effective reduction of SSB intakes has been met with many challenges.⁶ While their palatability, accessibility, publicity, affordability, and social acceptability contribute to frequent and sustained SSB consumption, their *caffeine and sugar content may further encourage continued intake*. Although adverse health consequences of excessive SSB consumption are well documented⁷, the extent to which their pleasant taste (due primarily to their sugar content) and post-ingestive effects (due to their sugar and/or caffeine content) positively reinforce consumption among children has not been elucidated. *It is particularly important to understand the determinants of caffeinated SSB use in children because beverage consumption habits in childhood will likely be sustained into adolescence and adulthood and will contribute to obesity and metabolic disease risk later in life*. This is particularly important to study among children from low-income and minority backgrounds, as these children have the highest rates of SSB intake and the highest prevalence of obesity.

Examining the feasibility of removing caffeinated SSBs and exploring whether this induces withdrawal symptoms among youth will enable us to investigate independent and combined effects of avoiding sugar, caffeine, or both, which will be integral to the design of a future larger scale intervention and to inform ongoing and future efforts for reducing SSB consumption. Findings will provide a comprehensive picture of the extent to which children are dependent on sugar and/or caffeine in SSBs and will inform whether their removal is feasible. If withdrawal symptoms are observed, this will have important implications for future efforts to limit consumption.

C. Preliminary Studies

Not applicable.

D. Research Design and Methods

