Beginning at the baseline visit (in person) and continuing daily throughout the intervention (online), participants will be asked to complete a child-adapted version of the validated Caffeine Withdrawal Symptoms Questionnaire (CWSQ). During the baseline visit, child participants will taste a small sample of each study beverage in pairs and will rate which beverage they like better and which beverage tastes sweeter using the enclosed beverage taste testing form. Child participants will be randomized into one of three study arms, where they will be instructed to replace their usual caffeinated SSBs with either: caffeinated SSB's provided by the study team, caffeine-free SSBs (caffeine-free Pepsi) or unsweetened sparkling water (LaCroix), compared to control (regular Pepsi consumption) for two weeks. All beverages will be provided by the study team, including drinks for the control group. After randomization, participants (child and parent together) will complete a daily online compliance questionnaire.

An outline of the schedule of study activities is below:

Time	Activity
Baseline Study Visit (Day 0) 1.5 hours	
 • Consent/assent • Height and weight • Complete in-person Caffeine Withdrawal Symptoms Questionnaire (CWSQ) with parent and child [this is called Daily Feelings Questionnaire in the Assent Form for kid-friendly language] • Dietary recall (parent and child)

	
 • Beverage taste testing (child) • Randomization and counseling regarding intervention (parent and child) • Provision of study beverages

Intervention (Days 1-14) Total of 1 hour per week
	
 • Parents receive three times weekly text message/email/phone reminders (based on participant preference) from study team • Parent and child together complete daily online CWSQ • Parent and child together complete daily online compliance survey • Child participant consumes assigned study beverages

Mid-intervention Visit Or Telephone Check-in (after first week of intervention)
 
~30-45 minutes
	
 • Complete in-person Caffeine Withdrawal Symptoms Questionnaire (CWSQ, parent and child together) • Dietary recall (parent and child together) • Provision of additional study beverages if needed • Participants and their parents encouraged to ask questions or express concerns

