
Follow-up visit (Day 15) 1.5-2 hours
	
 • Complete in-person Caffeine Withdrawal Symptoms Questionnaire (CWSQ, parent and child together) • Dietary recall (parent and child together) • Beverage taste testing (child participant) • Return empty study beverages • Qualitative interview (~20 minutes, parent and child together)

Details of all study procedures are described below:

Study Procedure	Description
Height and weight	Child participant's height and weight will be measured using a portable scale and stadiometer.
Caffeine Withdrawal Symptoms Questionnaire (CWSQ)	Parent and child participants will together complete a child-adapted version of the validated CWSQ ⁸ in person at baseline, and online daily throughout the intervention. [name] and/or a trained RA will assist with CWSQ completion at baseline and will counsel participants regarding filling out the online questionnaire.
24 hour dietary recalls	Participants will be asked (with the help of their parent) to report everything that they eat and drink over the past 24 hours. 24-hour recalls will be conducted at baseline (in person), after 1 week of the intervention (in person or via phone depending on participant preference), and at follow-up (in person).
Beverage taste testing	Prior to randomization, child participants will taste pairs each study beverage (10 mL) in randomized order and rate which beverage they like better and which beverage tastes sweeter using the taste enclosed taste testing form. Participants will rinse with water between each test. Taste testing will be completed in a private room and supervised by trained RAs. Child participants will also complete taste testing at follow-up.
Compliance questionnaires	Participants (child and their parent) will complete an online, 4-item questionnaire daily throughout the intervention to assess compliance (percentage of assigned beverages consumed, assessment of whether caffeinated SSB were consumed in violation of the study protocol, and if so, the brand and quantity consumed).
Randomization and Blinding	Following baseline assessments, child participants will be randomized using sex-stratified permuted block randomization into one of three arms: 1) caffeine-free SSBs (caffeine-free Pepsi) 2) unsweetened sparkling water (LaCroix) or 3) control (Pepsi).

	Assigned beverages will replace usual caffeinated SSB consumption, as assessed at enrollment.

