There are several potential limitations to our proposed study. The first is that successful recruitment and data collection with children presents unique challenges. However, we are recruiting from a large sample of children throughout the greater Washington metropolitan area and our team has extensive experience conducting research with children. Another challenge is that participants in the clinical study may consume caffeinated SSBs or other caffeine- and/or sugar-containing products, which would minimize the likelihood of observing withdrawal symptoms. We will account for this by assessing diet using 24-hour dietary recalls, as well as daily online compliance questionnaires. We also acknowledge that those who do not consume still/seltzer water may be opposed to consumption. However, we have successfully randomized seltzer water naïve participants to consume them previously. It is also possible that the opaque wrapper may be insufficient to maintain blinding of study beverage assignments. However, transferring commercially available carbonated beverages to a separate and unidentifiable container is not possible, as opening containers prior to consumption would result in lost carbonation and altered taste.

E. Study Population – (Gender and Minority Inclusions):

The subject population will be comprised of 60 children, both male and female, aged 8-11 (3rd to 5th grade) and their respective parent/legal guardian, for a total of 60 children and 60 parents. In addition to age range, inclusion criteria consists of reporting regular consumption of caffeinated sugar-sweetened beverages, defined in this study as consuming ≥ 12 ounces of caffeinated SSB's per day. Children under 8 years of age will be excluded to ensure that participants are able to adequately articulate their reasons for SSB consumption. Children who have a poorly managed chronic medical condition, a current or prior eating order diagnosis, or who report regular consumption (≥ 1 serving per week) of other caffeinated beverages, such as energy drinks, regular coffee, or hot tea will also be excluded to ensure that we are adequately able to evaluate study aims and outcomes.

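### The protocol relies on an opaque wrapper for blinding but names no blinded party, and daily compliance item 1, filled in literally, tells families in the two Pepsi arms which drink they were assigned

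*Protocol*

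**What the plan says.** Blinding appears in two places in the Protocol and nowhere in the SAP.

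- The limitations paragraph at the end of Section D concedes: "It is also possible that the opaque wrapper may be insufficient to maintain blinding of study beverage assignments". It adds that "transferring commercially available carbonated beverages to a separate and unidentifiable container is not possible", because opening the containers early would lose carbonation and alter the taste.
- The Randomization and Blinding row of the procedures table begins "Following baseline assessments, child participants will be randomized using sex-stratified permuted block randomization into one of three arms". It then lists caffeine-free Pepsi, LaCroix and Pepsi. Despite its heading, it names no blinded party and no masking method. The wrapper is not mentioned in the Beverage distribution row either.

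Item 1 of the Compliance Questionnaire (Section Q, Appendix) reads "Did you drink the assigned study beverages {insert specific type for participant per randomization} today", with a line beneath it for brand and name. Parent and child complete this form jointly each day after randomization, and they complete the CWSQ jointly as well. The reminder messages in the same appendix are neutral: they ask the child "to drink only the study drinks provided until" the follow-up date.

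The narrative in Section D, before the schedule of activities, says children will be instructed to replace their usual drinks, and it names the products. The wording of the counselling itself is not given.

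**The concern.** A wrapper that hides the product serves little purpose if an online form names the product every day. The CWSQ consists of self-rated feelings such as tiredness, grumpiness and headache, so what a family expects can influence what it reports.

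The stake is one contrast. Section B says the design "will enable us to investigate independent and combined effects of avoiding sugar, caffeine, or both" and calls this integral to planning a larger intervention. Pepsi against caffeine-free Pepsi is the only pair of arms that differs in caffeine alone, and Aim 2 includes that comparison. If both sets of families know what they are drinking, a higher CWSQ score on caffeine-free Pepsi could come from caffeine removal, from expecting withdrawal, or from both. The data could not tell these apart.

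**Working it through.** The documents state no figure to reproduce. The check is a comparison of texts, some counting, and one piece of algebra that shows why no bias figure should be quoted.

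1. **Is masking intended, and of whom?** The limitations paragraph worries that containers can be identified up to the point of drinking. That fits the people who handle and drink the product, so it implies that families are meant to be masked, but it does not say so. Limiting the point to the two Pepsi arms is an inference: unsweetened sparkling water can be recognised by taste whatever the wrapper.

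2. **What does item 1 disclose?** The placeholder calls for the participant's randomized type. Filled in literally, it names the drink. The brand line beneath discloses nothing by itself; it is a field that a masked family could not complete.

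3. **How many families?** The SAP (Statistical Design and Power) gives 20 per group. Two Pepsi arms × 20 = 40 of 60 families (40/60 = 67%).

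4. **When?** The form is daily on Days 1–14, so up to 14 showings per family. Peak withdrawal uses the first 72 hours, roughly Days 1–3, so about 3 showings fall inside the window.

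5. **Are the dietary recalls another route in that window?** The procedures table says "24-hour recalls will be conducted at baseline (in person), after 1 week of the intervention" and again at follow-up. The baseline recall precedes randomization and the other two fall after the window, so 0 of 3 recalls lie within it. Counselling at the baseline visit does come earlier and could disclose the arm.

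6. **Can the effect on the planned ANOVA be sized?** Suppose there is no true effect, and let d (in SD units) be the shift in families who know they have lost caffeine. The documents give no value for d. With n = 20 per arm, the noncentrality is λ = n × Σ(μᵢ − μ̄)². Arms are in the order control, caffeine-free, water.
   - Pepsi arms unmasked, means (0, d, d): Σ = (4/9 + 1/9 + 1/9)d² = (2/3)d², so λ = 13.33d². Caffeine-free minus control = d.
   - Pepsi arms masked with no expectancy, means (0, 0, d): Σ = (1/9 + 1/9 + 4/9)d² = (2/3)d², so λ = 13.33d². Caffeine-free minus control = 0.
   - Pepsi arms masked, each carrying half the expectancy, means (d/2, d/2, d): Σ = (1/36 + 1/36 + 4/36)d² = (1/6)d², so λ = 3.33d². Caffeine-free minus control = 0.

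   Whether masking changes the overall test therefore depends on what masked families expect, which is undocumented. The pairwise difference of d in the first pattern merely returns the assumption put in. No rejection rate drawn from such a model belongs in this point.

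**The case against.** The strongest reply is that the harm depends on two unstated conditions: that families are the masked party, and that the placeholder is filled with a product name. A neutral code might be entered instead. Families may also be meant to know their drink, in which case item 1 is correct and the blinding text is at fault. This stands, and it is why the conclusion is conditional. It does not remove the need for an edit, because on either reading the documents do not fit together.

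Second, the Section D instruction names the products, so families may learn their arm at randomization, before any daily form. If so, item 1 tells them nothing new. That also stands as a possibility. The named products may be a description for protocol readers and not the words spoken to families, so disclosure there is not established. The counselling has to be part of the fix.

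Third, the recruitment flyer tells all prospective families that the study involves sugar-free and/or caffeine-free drinks. Masked families may therefore expect some caffeine loss too. This is correct, and it is one reason why the bias cannot be sized.

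Fourth, the protocol already lists imperfect blinding as a limitation. That covers failure of the wrapper. It does not cover disclosure by the study's own form.

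**Conclusion.** The inconsistency is real. The protocol describes an attempt at blinding, does not say who is blinded, and includes a form that would defeat the blinding for Pepsi-arm families if they are its target and the form is filled in literally. The size that can be stated is 40 of 60 families and about 3 forms each within the 72-hour window.

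Two stronger readings are tempting and unsupported. A reader might infer that the trial is bound to unmask families; that requires both conditions above, and neither is stated. A reader might also infer either that the ANOVA's false-positive rate is inflated by some known amount, or that the overall test is untouched and only the pairwise contrast is at risk. Both need an assumed expectancy in masked families that the documents do not give.

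The weight is minor. The CWSQ is a secondary, exploratory outcome in a feasibility pilot, the definition of the primary compliance outcome does not change, and sparkling water cannot be masked in any case.

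**What to change.** State in the Randomization and Blinding row who is masked, in which arms and how. Then follow whichever branch applies.

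**If families in the two Pepsi arms are masked:**
- Reword item 1 in all arms to *Did you drink the study drinks provided today? How many?* Drop the inserted type, and drop the brand line under item 1 only. Leave items 2–4 as they are.
- Use the same neutral wording in the counselling at randomization.
- In the dietary recalls, record what the family reports. Do not fill in the product from the study ID: that would presume the adherence the recalls are meant to check, and compliance is the primary outcome. Check adherence with the returned empty containers and items 2–4.

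**If families are meant to know their drink:** correct the Randomization and Blinding row and the limitations paragraph, leave item 1 alone, and report the caffeine contrast on the CWSQ as unblinded.

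The cost is one item on one online form, one sentence in the procedures table and a check of the counselling wording, with no extra visits or staff. The downside is that item 1 would no longer record the named product or, in the sparkling-water arm, the flavor. The change removes one avoidable route of unmasking; it does not guarantee blinding.

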Beverage distribution	A two-week supply of beverages (corresponding to randomization and the amount of SSBs typically consumed) will be provided. If a participant runs out of beverages, the study team will provide additional beverages. Children will be counseled to drink only the study drinks provided or water and not to consume any other beverages during the two week intervention. Parents will also be counseled regarding encouraging their child to consume only the study beverages or water throughout the two week study period.
Compliance and reminders	Compliance will be assessed by collection of empty beverage containers. Empty containers will be picked up by the study team at the end of the intervention to minimize participant burden. If a participant is provided with additional beverages, empty containers will be requested prior to distribution of more beverages. Compliance will be further monitored during dietary recalls.
Mitigation of withdrawal symptoms	If a child experiences headaches, nausea, or other discomfort, they will be asked to report symptoms using the CWSQ before taking pain or anti-nausea remedies. Children and their parents will be discouraged from using over-the-counter medications, unless the severity of the symptoms are reported to be above a pre-determined threshold (rating of 4 or higher on the CWSQ Likert scale). In addition, participants will be strictly instructed not to use any pain remedy containing caffeine.

Data analysis:

Caffeine withdrawal scores will be collected using the CWSQ, completed by the child and parent together. Peak withdrawal symptoms will be operationalized as CWSQ scores reported within the initial 72 hours of the intervention, between the three groups. Univariate analyses and one-way ANOVA will be used to assess group differences in our primary (measures of compliance with beverage intervention) and secondary (withdrawal symptoms) study outcomes.

Dietary recalls will allow us to assess adherence to the study beverages as replacements for habitual caffeinated SSBs and to determine if caffeinated SSB removal impacts dietary choices. While we acknowledge limitations inherent to self-report dietary assessment, dietary recalls are sufficient for capturing beverage consumption data and will enable us to determine whether participants change their diet to compensate for caffeine restriction.

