Liking of study drinks may affect compliance and we will therefore run exploratory multivariable linear regression models including taste ratings as a potential confounder, along other potential covariates such as sex, race/ethnicity, age, weight, and volume of habitual SSB consumption. While we recognize that we are not sufficiently powered for multivariable regression models including a large number of covariates, these data will be critical in informing sample size calculations for our subsequent R01 proposal. We will use an intention to treat (ITT) approach and will minimize loss to follow-up by maintaining close contact with participants. All analyses will be conducted using SAS 9.4.

Dietary intake will be collected through dietary recall interviews (completed by the parent and child together). This will allow us to assess adherence to the study beverages as replacements for habitual caffeinated SSBs and to determine if caffeinated SSB removal impacts dietary choices. While we acknowledge limitations inherent to self-report dietary assessment, dietary recalls are sufficient for capturing beverage consumption data and will enable us to determine whether participants change their diet to compensate for caffeine restriction.

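### The Beverage Questionnaire has overlapping top frequency boxes, a top amount label that contradicts itself at 20 fl oz, and an example naming an unprinted box, so habitual volume may be misrecorded for some children

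*Protocol*

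**What the plan says.** The form is in the protocol, section Q (Appendix), under Beverage Questionnaire. It covers the past month and takes one frequency and one amount per drink; the frequency columns are headed "HOW OFTEN (MARK ONE".

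- The two highest frequencies are "2+ times per day" and "3+ times per day". The box below them is once per day.
- The two highest amounts are "16 fl oz (2 cups or 1 soda bottle" and "More than 20 fl oz (2 1/2 cups" (each label closes with a bracket).
- The first instruction gives the example "if you drank 5 glasses of water per week, mark 4-8 times per week". The printed grid has a box for 4-6 per week and none for 4-8.

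Usual intake is used in three places. In the procedures table of protocol section D, the randomization row says the assigned drinks replace usual caffeinated SSB intake as assessed at enrollment. In the same table, the beverage distribution row sets the two-week supply as "corresponding to randomization and the amount of SSBs typically consumed". The SAP (Statistical Design and Power), like the protocol's data analysis text, lists "volume of habitual SSB consumption" among possible covariates for exploratory regressions. None of these places names an instrument or a scoring rule.

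**The concern.** Closed response boxes should be mutually exclusive, and their labels should agree with themselves. Here the overlap falls at the top of the frequency scale, and this trial enrolls children who drink at least 12 oz of caffeinated SSB a day (protocol section E). Many of them will answer in that part of the grid. Once a child has marked the lower of the two overlapping boxes, the form cannot show whether the true frequency was two or three or more.

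What is at stake is the quality of the habitual-volume variable. Children are not assigned a number of drinks; they replace what they usually drink. The total number of study drinks consumed, one of the compliance measures, is therefore easier to interpret when usual volume is known accurately. Both documents also say the exploratory models are meant to inform sample size for a later grant proposal.

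**Working it through.** The plan gives no figure for habitual intake, so there is none to reproduce. The check covers the labels and the size of a possible misrecording.

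**Inputs from the documents:** the box labels and the example above; a 14-day intervention (section D); entry at 12 oz/day or more (section E). **Assumed:** 12 oz per occasion, with a range of 8 to 20 oz; 8 fl oz per cup, which is the form's own equivalence; and a child drinking three times a day who marks the lower overlapping box and is scored as two a day.

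**1. Frequency overlap.** Three or more is a subset of two or more, so every child at three or more a day fits both boxes.
- Scored as two: 2 × 12 = 24 oz/day. Over 14 days, 24 × 14 = 336 oz, and 336/12 = 28 cans.
- Scored as three: 3 × 12 = 36 oz/day. Over 14 days, 36 × 14 = 504 oz, and 504/12 = 42 cans.
- Shortfall: (36 − 24)/36 = 33%, or 14 cans.
- Range: 16 vs 24 oz/day at 8 oz per occasion; 40 vs 60 oz/day at 20 oz. The percentage is the same throughout.

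**2. Top amount.** 2.5 cups × 8 = 20 fl oz exactly, while the label says more than 20. A 20-oz drinker matches the cup figure but not the ounce figure, and the next box down is the one labelled as a soda bottle. If a 20-oz bottle is marked as 16 oz, the error is (20 − 16)/20 = 20%. At one a day for 14 days, that is 14 × 16/12 = 18.7 cans instead of 14 × 20/12 = 23.3.

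**3. Where eligible children answer.** At 12 oz per occasion, six times a week is 6 × 12/7 = 10.3 oz/day, below the entry threshold, and once a day is 12 oz/day. At that serving size an eligible child can only be in the once-a-day box or one of the two overlapping boxes. With larger servings the 4-6 per week box can also qualify (6 × 16/7 = 13.7 oz/day).

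**4. Example.** Five per week belongs in the printed 4-6 box. At 12 oz that is 5 × 12/7 = 8.6 oz/day, so this slip is not about heavy drinkers.

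**The case against.** The strongest reply is that the form's consequences are not established.

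- **Source.** Nothing in either document says that this form provides the usual intake. The protocol also mentions a screener questionnaire (section D), an enclosed eligibility checklist (section F) and a beverage screener (section G), and the section D schedule does not list the Beverage Questionnaire. This stands. The link is an inference from its being the only enclosed form that records habitual volume; the baseline recall covers just 24 hours.
- **Reading of the boxes.** Told to mark one box in an ordered row, many respondents will take the lower box as two and the upper as three or more. The cup figure may likewise steer 20-oz drinkers to the top amount. This also stands, so the percentages describe what can happen to an individual answer, not an expected bias.
- **Gaps between amounts.** A reader might infer that sizes such as 6-7 oz have no box. The instructions ask for an approximate amount, so the middle boxes act as anchor points and such servings go to the nearest one. That is not a fault.
- **Supply.** The beverage distribution row provides more drinks when a child's stock is used up. At three a day, 28 cans last 28/3 = 9.3 days, and the rule covers the rest. With no fixed number assigned, oversupply does not change the instruction. The rule does not correct the recorded volume.
- **Analyses.** Compliance is measured by daily logs, supported by empty containers and recalls. The one-way ANOVAs of the primary and secondary outcomes do not use habitual volume. It enters only exploratory models that the plan itself calls underpowered.

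What remains is that the labels are wrong as printed and that an ambiguous answer cannot be resolved from the form afterwards.

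**Conclusion.** The three label faults are certain from the text. Their effect is possible, not shown: habitual volume may be up to 33% low for a child drinking three times a day and 20% low for a 20-oz bottle marked as 16 oz. These sizes rest on the assumed serving and scoring, and the documents give no basis for estimating how many children are affected. The example slip is a simple correction, since the intended box is obvious.

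A reader might go further and infer that intake is misread for heavier drinkers as a matter of course, that the supply is therefore mismatched, that the primary outcome is compromised, or that the weakened covariate would have explained most of the spread in drinks consumed. The documents support none of these. They name no source instrument, they provide for top-up, they keep the variable out of the ANOVAs, and they say nothing about how much variation it explains. This is a minor data-quality point, worth correcting because the correction is cheap.

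**What to change.** 1. Relabel the second-highest frequency as exactly 2 times per day and keep the box for three or more.
2. Relabel the largest amount as 20 fl oz or more (2 1/2 cups or more).
3. Change the example so that it names the printed 4-6 per week box.
4. Optionally, on the caffeinated soda and sweet tea rows, add a write-in of number per day and container size. Compute habitual caffeinated SSB ounces per day from it, for both the supply and the covariate. Relabelling alone leaves the top boxes open-ended; the write-in removes that limit too.
5. State in the SAP which instrument and scoring rule define habitual volume.

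The cost is a minor amendment to an IRB-approved form and a sentence in the SAP, best made before or early in enrollment. Answers already collected on the present form would not match the new boxes exactly, so any such records should be flagged by form version.
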